Few postmarketing reports of new-onset or worsening diabetic macular edema with decreased visual acuity have occurred with TZDs, including pioglitazone. Many of these patients reported concurrent peripheral edema. It is not known whether there is a direct association between pioglitazone and macular edema, but investigators should be alert to the possibility of macular edema. If study participants report disturbances in visual acuity (eg, blurred vision, distortion of images, missing areas, dimming or “graying-out” of vision from loss of contrast sensitivity, and changes in the way color is perceived), they will be evaluated by an ophthalmologist.

There have been postmarketing reports of bone fractures associated with the use of TZDs, including pioglitazone. The majority of the fractures occurred in women with most of the fractures involving upper and lower limbs of the body. Many cases lack any information about history or about risk factors for bone fractures. In cases where information was available, patients had a history of and multiple risk factors for fractures.

Adverse events associated with pioglitazone, listed in the Warnings and Precautions section of the Company Core Data Sheet [20], for subjects with T2DM and at doses considerably higher (15-45 mg) than the intended dose in this clinical development program (sustained release [SR] 0.8 mg) were as follows: congestive heart failure (CHF) and peripheral edema due to dose-related fluid retention, hepatic failure, increased incidence of fractures in female population, hypoglycemia, macular edema, and bladder cancer. A detailed discussion of the safety profile of pioglitazone is provided in the investigator’s brochure.

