7.5 Procedures for Discontinuation or Withdrawal of a Subject

The investigator may terminate a subject's study participation at any time during the study when the subject meets the study termination criteria described in Section 7.4. In addition, a subject may discontinue his or her participation without giving a reason at any time during the study. Should a subject's participation be discontinued, the primary criterion for termination must be recorded. In addition, efforts should be made to perform all procedures scheduled for the EW Visit. Discontinued or withdrawn subjects will not be replaced.

Subjects who discontinue study medication prematurely should be contacted by the study site every 6 months until the conclusion of the study via telephone to assess the general well-being of the subject as well as to obtain any changes in medications related to cognitive health. In the event the subject is not able to be reached, the subject's caregiver or primary care physician can be contacted to obtain this information.

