10.2 Procedures

10.2.1 Collection and Reporting of AEs

10.2.1.1 PTE and AE Collection Period

Collection of PTEs will commence from the time the subject signs the informed consent to participate in the study and continue until the subject is first administered study medication (Study Visit 3) or until screen or baseline failure. For subjects who discontinue prior to study medication administration, PTEs are collected until the subject discontinues study participation.

Collection of AEs will commence from the time that the subject is first administered study medication (Study Visit 3). Routine collection of AEs will continue until 2 weeks after completion or withdrawal from the study (safety Follow-up Visit).

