4. Bone fractures: All female subjects, regardless of their clinical risk factors for osteoporosis, should be encouraged to eat a balanced diet and participate in appropriate exercise, avoid cigarette smoke and excessive alcohol consumption. All postmenopausal women should be encouraged to employ lifestyle practices that reduce the risk of bone loss and osteoporotic fractures: maintaining a healthy weight, eating a balanced diet, obtaining adequate calcium and vitamin D, participating in appropriate exercise, avoiding excessive alcohol consumption, not smoking. An adequate intake of both calcium and vitamin D is important for bone health and is recognized as an important component of any osteoporosis prevention drug regimen [68]. Among women age 75 and older, muscle strengthening and balance exercises have been shown to reduce the risk of falls and fall-related injuries by 75% [69]. Weight-bearing exercise can be as simple as brisk walking. All suspected or confirmed bone fracture will be followed-up for an X-ray confirmation, outcome, and any healing complications. Current standards of care for assessing and maintaining bone health will be applied.
5. Bladder cancer: Subjects and their project partners will be advised to promptly report any signs or symptoms that could be consistent with bladder cancer such as hematuria, urinary urgency, urinary frequency, or dysuria. Any subject with previous or active bladder cancer

will be excluded. All subjects will be screened for evidence of hematuria (macroscopic or microscopic). In the event of unexplained hematuria (3 or more red blood cells per high power field on microscopic urine test), confirmed by a repeat test (within 14 days of the initial assessment), subject will be referred to a urologist for additional follow-up testing according to local standard diagnostic approach. If the diagnosis of the bladder cancer cannot be excluded the subject will be withdrawn from the study.

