Clarity has been provided to the assessments conducted during CMFVs. The required timing of MRI scans performed at CMFVs has been clarified and the requirement to perform multiple MRI scans within a short period of time, which adds to subject burden, has been removed.

Erroneous text stating that two consecutive diagnoses by the investigator are required to reach an outcome of MCI due to AD has been removed. Two consecutive diagnoses of MCI due to AD by the CIAC are required for the subject to meet endpoint and it is possible that these diagnoses differ from the investigator's.

Page 56, Section 7.5, Procedures for Discontinuation or Withdrawal of a Subject

Existing Text

Subjects who discontinue study medication prematurely should be contacted by the study site every 6 months until the conclusion of the study via telephone to assess the general well-being of the subject as well as to obtain any changes in medications. In the event the subject is not able to be reached, the subject's caregiver or primary care physician can be contacted to obtain this information.

Revised Text

Subjects who discontinue study medication prematurely should be contacted by the study site every 6 months until the conclusion of the study via telephone to assess the general well-being of the subject as well as to obtain any changes in medications **related to cognitive health**. In the

event the subject is not able to be reached, the subject’s caregiver or primary care physician can be contacted to obtain this information.

Rationale for Amendment

This revision more accurately describes the limited information that will be collected during 6 monthly telephone follow-up calls for subjects who have discontinued study drug

Page 66, Section 9.1.8, Procedures for Clinical Laboratory Samples

Existing Text

Table 9.a Clinical Laboratory Tests

Hematology	Serum Chemistry	Urinalysis (c)
Red blood cells	Alanine aminotransferase	pH
White blood cells count with differentials (Neutrophils, Eosinophils, Basophils, Lymphocytes, Monocytes)	Alkaline phosphatase Aspartate aminotransferase Total bilirubin Direct bilirubin (a) γ-Glutamyl transferase	Specific gravity Protein Glucose Blood Nitrite
Hemoglobin	Total protein	
Hematocrit	Albumin	
Platelets	Creatinine	
HbA1c (b)	Blood urea nitrogen Potassium Sodium Glucose Calcium, PTH TSH, free T4 Vitamin B12, folate (d) Rapid plasma reagin (RPR) (d)	
Blood		
Hepatitis panel, including HBsAg and anti-HCV (b)		

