In general, the baseline value for a variable is defined as the last observation prior to the first dose of double-blind study medication (visit date \leq first dose date), including the screening value, if necessary.

Adverse events that start more than 30 days after the last dose of double-blind study medication (start date – last dose date >30) will be listed, but excluded from the summaries and analyses. For efficacy and other safety data, data that are obtained more than 7 days after the last dose of double-blind study medication (visit date – last dose date > 7) will be listed, but excluded from summaries and analyses. (Note: This efficacy data window only applies to determining which data are included/excluded from the summary statistics and formal statistical analysis tables for a given efficacy endpoint. All events of MCI due to AD (or AD dementia) as determined by the adjudication committee will be included in the time-to-event analyses, without regard to the date of last dose of double-blind study medication.)

If the date of first dose of double-blind study drug collected in the eCRF is missing, then for summary purposes the day after the first dispense date will be used as an estimate for the date of first dose. However, if all dispensed study drug is returned, then the subject is assumed to have not taken any study drug, and the first dose date will not be imputed.

If the date of last double-blind study drug dose collected in the eCRF is missing, then the earliest of the following dates will be used for the last dose date for analysis and summary purposes: date of death, date of last visit (recorded in the eCRF), last double-blind study drug return date, and the last double-blind study drug dispense date (following the last drug return date) + 200 days (ie, the double-blind study drug dispensing interval corresponding to the number of study drug tablets dispensed).

The study window convention will not be applied to the eCRF data listings. The data listings for eCRF data will display the raw data as collected and entered in the eCRF. For efficacy listings, windowed visits will also be shown on the listings.

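### Bladder cancers first found after a subject leaves are not actively collected beyond 2 weeks, and those starting over 30 days after last dose are listed but not summarized

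*Protocol*

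**What the plan says.** **The risk.** Protocol 4.1 ends its list of the drug's labelled warnings with "hypoglycemia, macular edema, and bladder cancer". Protocol 10.2.1.3 and SAP 9.14.1 make bladder cancer an AESI.

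**Suspected cases.** After unexplained hematuria is confirmed on repeat testing, the "subject will be referred to a urologist for additional follow-up testing according to local standard diagnostic approach". Then: "If the diagnosis of the bladder cancer cannot be excluded the subject will be withdrawn from the study" (Protocol 10.2.1.3).

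**Collection after leaving.** "Routine collection of AEs will continue until 2 weeks after completion or withdrawal from the study" (Protocol 10.2.1.1). The 6-monthly calls that continue to study end are made "to assess the general well-being of the subject as well as to obtain any changes in medications related to cognitive health" (Protocol 7.5; Appendix A note j says the same). Protocol 10.2.2 makes an SAE that surfaces after the collection period reportable only if it is volunteered and thought related to study participation.

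**Tabulation.** SAP 9.1.3: "Adverse events that start more than 30 days after the last dose of double-blind study medication", with the start date as the test, "will be listed, but excluded from the summaries and analyses". SAP 9.14.1 repeats the rule and admits only treatment-emergent events to summary tables. Its AESI summary has no exemption.

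**Provisions that work the other way.** Protocol 10.2.1.2 requires subjects with an AE to be monitored until it subsides or is satisfactorily explained. Protocol 10.3 follows SAEs to a permanent outcome. SAP 9.14.1 lists all AEs, with separate listings for AESIs, SAEs and deaths.

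**The concern.** A cancer that begins during treatment can be diagnosed after the subject has left. This trial has long exposure, and its own planning assumption is that nearly half the subjects leave within 5 years. For those subjects the site stays in telephone contact but has no instruction to ask about an event the protocol names as a risk.

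The AESI table is where a reader will look for the comparison between arms. If leaving is unrelated to treatment and to risk, missed cases thin both arms alike and the comparison loses information. If leaving is related to either, the comparison can also shift. For example, if the drug did raise the risk, withdrawals on suspicion would be more frequent on pioglitazone, and whatever goes uncounted after them would tend to favour the drug.

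**Working it through.** **1. The two windows do not match.** Active collection ends 14 days after withdrawal (Protocol 10.2.1.1). The treatment-emergent window runs to 30 days after last dose (Protocol 13.1.6, SAP 9.14.1). When last dose and withdrawal coincide, 30 − 14 = 16 days fall inside the table window although nobody is asking.

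**2. Two routes to a late diagnosis.**

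- *Cancer first found after leaving for another reason.* No AE is open, so the monitoring rule of 10.2.1.2 has nothing to act on. After day 14 the only route is a volunteered SAE judged related. If recorded with a start date past day 30, it is listed only.
- *Cancer suspected before withdrawal and confirmed afterwards.* The hematuria AE is open and must be followed to an explanation. Protocol 10.1.3 asks for one diagnosis per event but does not fix the date when a sign later becomes a diagnosis. If the event is updated and keeps its on-treatment onset, it is tabulated. If a new event is entered with a start past day 30, it is listed only. The documents do not say which applies.

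The dating question can matter. Suppose, for illustration, that new start dates follow last dose with an exponential delay of mean m days. The share past day 30 is exp(−30/m): 37%, 61% and 72% for m = 30, 60 and 90. The documents give no such delay, so these are assumptions.

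**3. How much follow-up is affected.** Inputs: 12% annual drop-out, 47% over 5 years (Protocol 13.3, SAP 8.0); durations of 4 years (Protocol 6.1 minimum), 5 years (the planning horizon) and 5.5 years (SAP Table 9.a, note d).

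- Plan's figure: 1 − 0.88^5 = 0.472, which reproduces 47%.
- Constant hazard: λ = −ln 0.88 = 0.1278 per year.
- Mean time on study over T = 5: (1 − e^(−λT))/λ = 0.472/0.1278 = 3.69 years.
- Time after leaving: 5 − 3.69 = 1.31 years per subject; 1.31/5 = 26%.

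Share of person-time after leaving, under both readings of 12%:

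| T (years) | λ = 0.1278 | λ = 0.12 |
|---|---|---|
| 4 | 0.869/4 = 21.7% | 0.823/4 = 20.6% |
| 5 | 1.306/5 = 26.1% | 1.240/5 = 24.8% |
| 5.5 | 1.550/5.5 = 28.2% | 1.474/5.5 = 26.8% |

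The range is therefore 21–28%. In a pioglitazone arm of 1,470, the 5-year figure is 1,470 × 1.306 ≈ 1,920 person-years.

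A subject who leaves within 5 years is off study for 1.306/0.472 = 2.76 years on average. The 14-day collection covers (14/365.25)/2.76 = 1.4% of that time, and the 30-day table window 3.0%.

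**The case against.** **Suspected cases are protected.** A reader might infer that a subject withdrawn for suspected bladder cancer is lost to the safety data. The documents do not support that. Withdrawal follows confirmed hematuria and a urology referral. The open AE must be monitored to an explanation with no 2-week limit, and SAEs are followed to a permanent outcome. AESIs are reported promptly whatever their seriousness or causality, and treatment-emergent AEs leading to discontinuation have their own table. This objection stands. What remains for such cases is the undefined onset date.

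**The cut-off is on start date.** A reader might also infer that any diagnosis made after day 30 is cut. It is not: a cancer that presented as on-treatment hematuria can keep that onset and be tabulated. This stands too.

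**Late events stay visible.** Recorded events are listed by treatment, and the DSMB reviews all safety data (Protocol 11.2). This stands in part, since listings and DSMB packages contain only what was collected.

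**The limits are deliberate.** The 30-day window is the same in both documents. The safety objective concerns the treatment period (Protocol 5.1.3.1). Appendix J says the call text was revised to describe "the limited information that will be collected during 6 monthly telephone follow-up calls". Protocol 4.1 ties the warning to diabetic subjects at much higher doses. These are reasons to keep the 30-day table and to avoid alarm. They do not explain why calls already being made should leave out an event the sponsor itself chose to track.

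**Conclusion.** The point holds for bladder cancers first found after a subject has left. They are not actively sought beyond 2 weeks, the late route depends on a volunteered report judged related, and those starting past day 30 cannot enter the AESI summary. For a case suspected before withdrawal, the fault is narrower: the plan does not say how a later-confirmed cancer is dated.

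Up to about 26% of 5-year person-time (21–28% over the durations and drop-out readings tried) has no active AE collection. This is a ceiling. It assumes a constant drop-out hazard, ignores conversions and deaths, and treats every leaver as reachable. Protocol 7.4 counts loss to follow-up and voluntary withdrawal among the reasons for leaving. Where consent is withdrawn, Protocol 9.3.7 keeps even the safety call out of the (e)CRF.

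A reader might go further and infer that so few cases are expected that one or two would reverse the comparison, or that bladder cancer declares itself more slowly than the other AESIs. The documents give no expected case count and no latency, and the conclusion needs neither. It rests on the sequence of collection rules and is worth acting on because the remedy is cheap.

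**What to change.** 1. **Protocol 7.5 and Appendix A note j.** Add two fixed yes/no items to the existing 6-monthly calls: new bladder cancer, and death. Record the answers in the (e)CRF regardless of causality, where consent allows.
2. **Dating rule (Protocol 10.1.3 or 10.2.1.2, with SAP 9.14.1).** State that a cancer confirmed from a sign that began on treatment keeps that sign's onset date.
3. **SAP 9.1.3 and 9.14.1.** Keep the 30-day table unchanged. Beside it, add one supplementary table of all bladder cancers from first dose to study end, by randomized group, each labelled on- or off-treatment. The other safety tables go by treatment received (SAP 9.3), so the title should state the difference.

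The cost is two questions on calls already planned, one (e)CRF form, a sentence on dating and one table. The downside is that some cases will be recorded long after last dose, where attribution is weaker; the label deals with that. The withdrawal rule and all other clinical rules stay as they are.

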8.0 CLINICAL TRIAL MATERIAL MANAGEMENT

This section contains information regarding all medication and materials provided directly by the sponsor, and/or sourced by other means, that are required by the study protocol, including important sections describing the management of clinical trial material.

8.1 Study Medication and Materials

8.1.1 Dosage Form, Manufacturing, Packaging, and Labeling

In this protocol, the term study medication refers to all or any of the drugs defined below. AD-4833 SR 0.8 mg Tablets and placebo will be provided in high density polyethylene (HDPE) bottles containing a desiccant. The active formulation contains drug substance and excipients and the placebo formulation contains excipients only. These tablets are for oral administration.

8.1.1.1 Investigational drug

AD-4833 Tablets Placebo

AD-4833 tablet placebo is manufactured by Takeda Pharmaceutical Company Limited, Osaka, Japan. The oral administration tablets are pale red plain tablets. Each HDPE bottle contains 100 tablets and a desiccant and has a child resistant cap. The bottles will be labeled with a single panel or booklet label that will contain pertinent study information in local languages.

AD-4833 SR 0.8 mg Tablet

AD-4833 SR 0.8 mg Tablet is manufactured by Takeda Pharmaceutical Company Limited, Osaka, Japan. The oral administration tablets are pale red plain tablets. Each HDPE bottle contains 100 tablets and a desiccant and has a child resistant cap. The bottles will be labeled with a single panel or booklet label that will contain pertinent study information in local languages.

8.1.1.2 Sponsor-Supplied Drug

Sponsor-supplied drugs referenced in other sections of the protocol include the following: AD-4833 tablet placebo and AD-4833 SR 0.8 mg Tablet.

8.1.2 Storage

All clinical trial material must be kept in an appropriate, limited-access, secure place until it is used or returned to the sponsor or designee for destruction. All sponsor-supplied drugs must be stored under the conditions specified on the label, and remain in the original container until dispensed. A daily temperature log of the drug storage area must be maintained every working day.

CONFIDENTIAL

8.1.3 Dose and Regimen

This is a placebo-controlled, double-blind, parallel group study comparing AD-4833 SR 0.8 mg Tablet to Placebo. Subjects will be randomized in a blinded fashion to one of the following within the following two subject groups, Non-Hispanic/Latino Caucasian and Non-Caucasian or Hispanic/Latino Caucasian.

Table 8.a describes the dose and tablet count that will be provided to each group.

Table 8.a Sponsor-Supplied Drug

Treatment Group	Dose	Treatment Description	
		Active	Placebo
1	Placebo QD	Zero active tablets	One AD-4833 tablet placebo
2	AD-4833 SR 0.8 mg Tablet QD	One AD-4833 SR 0.8 mg tablet	Zero placebo tablets

